### 12.2 Data Monitoring Committee

A data monitoring committee (DMC) consisting of external physicians with an expertise in Endocrinology and the management of insulin-requiring diabetes including CGM, along with an external statistician will be convened to review study progress and safety. The Board will convene approximately every 90 days. The Board will also meet when ad hoc review is required.

#### The DMC will perform 4 main functions:

**First:** DMC will track and trend the overall safety of the study.

D00409632 Version E Page 87 of 106

Event rate, defined as number of events per 100 patient years, will be reviewed by the DMC with respect to the following:

- Event rate of all SAEs
- Event rate of severe hypoglycemia
- Event rate of severe hyperglycemia
- Event rate of DKA
- Event rate of device related AEs

Second: Based on their meetings, DMC will recommend a decision to the sponsor regarding the followina:

- Whether or not enrollment should be halted.
- Whether or not the entire study will need to be stopped including for those subjects who have received study devices already.

Note: If it is decided to withdraw subjects from participation in the study or if the study is stopped, subjects will be followed-up in accordance with standard practice by their own providers.

**Third:** During the study, the following steps will be taken for:

- Unanticipated adverse device effects (UADE)
- Device related DKA
- Device related severe hypoglycemia

DMC is to meet within 10 days from the time that the CEC adjudicates an event as one of the above. If possible, the investigator should be available to answer questions by DMC.

Based on their meetings, DMC will recommend a decision to the sponsor regarding the following:

- Whether or not enrollment should be halted.
- Whether or not the entire study will need to be stopped including for those subjects who have received study devices already.

Note: If it is decided to withdraw subjects from participation in the study or if the study is stopped, subjects will be followed-up in accordance with standard practice by their own providers.

Fourth: The DMC will review Safety data and provide a recommendation to the sponsor regarding staged enrollment of pediatric subjects:

The DMC will provide a recommendation to proceed with the following staged enrollment:

Enrollment of pediatric subjects 7-17 years of age into the study may not proceed until N=10 subjects 18 years of age or older have completed 30 days of the study period and the Data Monitoring Committee (DMC) has determined it is safe for subjects 7-17 years of age to be enrolled in the study.

General guidance for DMC's recommendations to sponsor should be based on the following: In general, a DMC recommendation regarding study stoppage or resumption of enrollment should be made to the sponsor within 1 week of the DMC meeting where the determination is made. However, if

more data is needed, the DMC may meet again to re-assess their decision within 2 weeks or when required data becomes available.

In their recommendation to the sponsor, the DMC may take into account the thresholds listed below for the number of subjects experiencing hypoglycemia requiring assistance from another person or DKA to identify when the number of subjects experiencing these events exceeds the number that would be anticipated for the study population over the duration of this study. These thresholds should be interpreted with caution due to potential differences in study populations and study design.

- a. Rates taken from type 1 exchange (Cengiz et. Al, and Weinstock et. Al), are higher than the clinical studies STAR 3, 530G adult in-home study (CEP266) and 530G Pediatric inhome study (CEP287).
- b. Reasons for lower rates of severe hypoglycemia and DKA in the clinical studies mentioned could be related to several factors including but not limited to the exclusion of those with DKA or severe hypoglycemia, additional attention secondary to mandatory study visits, selection bias of motivated patients willing to perform study procedures and access to free study devices during the course of the study.
- c. The DMC should consider stopping study if rates of severe hypoglycemia and DKA are significantly worse (e.g., higher) in AHCL than rates provided by clinical trials mentioned in **Table 5**.
- d. Age consideration may also be factored in by the DMC. For example, severe hypoglycemia rates in those >25 years may be higher than those 25 years and below.
- e. Should DKA and/or severe hypoglycemia occur early in the study, the DMC should consider that the higher event rate may not necessarily represent a significant safety concern.

Table 5. Hypoglycemia/ Hyperglycemia/ DKA Threshold

Adverse Event	Reference	Reference Rate > 25 years old	Reference Rate 15-25 years old	Reference Rate <15 years old
Severe Hyperglycemia events per 100 patient years	CER 302	NA	NA	71.64
DIVA suspete a su	STAR 3 Bergenstal et. al	SAP arm: 0.68 Control arm: 0	SAP arm: 2.7 Control arm: 3.6	SAP arm: 2.2 Control arm: 0
DKA events per 100 patient years	530G Adult in-home study CEP 266 (MDT on file)	1.27	3.4	N/A
	Pediatric in-home study CEP 287 (MDT on file)	N/A	N/A	0

Adverse Event	Reference	Reference Rate > 25 years old	Reference Rate 15-25 years old	Reference Rate <15 years old
	Type 1 exchange Weinstock et. al	4.8	N/A	N/A
	Type 1 exchange Cengiz et. al	N/A	9.9	9.9
	STAR 3 Bergenstal et. al	SAP arm: 16.5 Control arm: 20.9	SAP arm: 5.4 Control arm: 3.9	SAP arm: 10.2 Control arm: 3.6
Severe hypoglycemia per 100 patient years	530G Adult in-home study CEP 266 (MDT on file)	0.85	0	N/A
	530G Pediatric in-home study CEP 287 (MDT on file)	N/A	N/A	1.42
	Type 1 exchange Weinstock et. al	11.8	N/A	N/A
	Type 1 exchange Cengiz et. al	N/A	6.2	6.2

### **Device Deficiencies and Troubleshooting**

The Medtronic 24-Hour Technical Support (TS) will be consulted for device troubleshooting (e.g., assistance is needed by subject to operate their device[s]). When subjects call the TS, they are instructed to notify the TS operator that they are currently participating in a clinical research study. All device deficiencies that are reported to the TS will be documented by the TS staff.

The investigational center will be provided with a copy of all TS calls for their subjects. The TS call reports should be reviewed for investigational center staff awareness and assessment for the possibility of an AE. If an AE is detected the investigational center staff will complete the appropriate eCRF(s).

All device deficiencies reported directly to the investigational center staff by a subject should either be reported to the TS by the subject or investigational center staff. Any device deficiency the investigational center may have should be reported to the TS.

#### Device Deficiency (ISO 14155:2020)

A device deficiency is any inadequacy of a medical device with respect to its identity, quality, durability, reliability, usability, safety, or performance.

Note 1 to entry: Device deficiencies include malfunctions, use errors, and inadequacy in the information supplied by the manufacturer including labeling.

Note 2 to entry: This definition includes device deficiencies related to the investigational medical device or the comparator.

To return a study device as part of a device deficiency, the investigational center staff and/ or subject are required to call the 24-Hour TS. Following the call to TS, the investigational center staff should then follow the study procedures for returning products with device deficiencies.

It is the responsibility of the investigator to follow their IRB reporting requirements.

#### **Statistical Design and Methods 14.**

#### 14.1 General Aspects of Analysis

All data collected from the time of screening until the end of the study will be collected on eCRFs, subject questionnaires, and electronically by uploading the various devices. Data and analysis will be summarized in a Clinical Study Report. Any deviations from original statistical plan and the rationale will be described in the Clinical Study Report.

#### 14.2 Subject Disposition

The number of subjects enrolled, completed, and early terminated in the study will be presented. The reasons for discontinuing prior to study completion will be summarized.

### **14.3 Subject Demographics and Baseline Characteristics**

Subject characteristics, including age, gender, race, ethnicity, medical diagnosis, height, weight, BMI, and baseline HbA1c will be summarized by descriptive statistics (mean, standard deviation, minimum, median, and maximum) for continuous variables and by counts and percentages for categorical variables.

D00409632 Version E

Page 91 of 106

### 14.4 Endpoints and Hypotheses

### 14.4.1.1 Primary Safety Endpoint

#### Age 18-80:

• The overall mean change in HbA1c,  $\Delta\mu_{780G}$ , from baseline to end of 3-month study period will be estimated and compared to the threshold of -0.50% with a margin of 0.4%. A significance level of 0.025 (one-sided) will be used.

The hypothesis is mathematically expressed as:

$$H_0$$
:  $\Delta \mu_{780G} \ge -0.50\% + 0.4\%$ 

Ha: 
$$\Delta\mu_{780G} < -0.50\% + 0.4\%$$

#### Age 7-17:

• The overall mean change in HbA1c,  $\Delta\mu_{780G}$ , from baseline to end of 3-month study period will be estimated and compared to the threshold of -0.38% with a margin of 0.4%. A significance level of 0.025 (one-sided) will be used.

The hypothesis is mathematically expressed as:

$$H_0: \Delta \mu_{780G} \ge -0.38\% + 0.4\%$$

$$H_a$$
:  $\Delta \mu_{780G} < -0.38\% + 0.4\%$ 

### **14.4.1.2** Primary Effectiveness Endpoint

#### Age 18-80:

• The mean % of time,  $\mu_{780G}$ , in range (TIR 70-180 mg/dL) will be estimated and compared to the threshold of 73.7% with a margin of -7.5%. A significance level of 0.025 (one-sided) will be used.

The hypothesis is mathematically expressed as:

 $H_0$ :  $\mu_{780G} \le 73.7\% - 7.5\%$ 

 $H_a \colon \mu_{780G} > 73.7\% - 7.5\%$ 

#### Age 7-17:

• The mean % of time,  $\mu_{780G}$ , in range (TIR 70-180 mg/dL) will be estimated and compared to the threshold of 65.3% with a margin of -7.5%. A significance level of 0.025 (one-sided) will be used.

The hypothesis is mathematically expressed as:

H0:  $\mu_{780G} \le 65.3\% - 7.5\%$ 

 $H_a$ :  $\mu_{780G} > 65.3\% - 7.5\%$ 

D00409632 Version E Page 92 of 106

#### **Analysis of Secondary Effectiveness Endpoints** 14.4.1.3

#### Age 18-80:

Secondary Effectiveness Endpoint: The mean % time,  $\mu_{780G}$ , in hypoglycemia (< 54 mg/dL) will be estimated and compared to the threshold of 0.86% with a margin of 2%. A significance level of 0.025 (one-sided) will be used.

The hypothesis is mathematically expressed as:

H0:  $\mu_{780G} \ge 0.86\% + 2\%$  $H_a$ :  $\mu_{780G} < 0.86\% + 2\%$ 

Secondary Effectiveness Endpoint: The mean % of time, μ780G, in range (TIR 70-180 mg/dL) will be estimated and compared with a significance level of 0.025 (one-sided).

The hypothesis is mathematically expressed as:

H0:  $\mu_{780G}$  ≤73.7%  $H_a$ :  $\mu_{780G} > 73.7\%$ 

#### Age 7-17:

Secondary Effectiveness Endpoint: The mean % time,  $\mu_{780G}$ , in hypoglycemia (< 54 mg/dL) will be estimated and compared to the threshold of 0.71% with a margin of 2%. A significance level of 0.025 (one-sided) will be used.

The hypothesis is mathematically expressed as:

 $H_0$ :  $\mu_{780G} \ge 0.71\% + 2\%$  $H_a$ :  $\mu_{780G} < 0.71\% + 2\%$ 

Secondary Effectiveness Endpoint: The mean % of time, μ780G, in range (TIR 70-180 mg/dL) will be estimated and compared with a significance level of 0.025 (one-sided).

The hypothesis is mathematically expressed as:

H0:  $\mu_{780G}$  ≤65.3%  $H_a$ :  $\mu_{780G} > 65.3\%$ 

### **14.4.2 Descriptive Endpoints**

- Time spent in the SmartGuard feature versus time spent in Manual Mode
- Change in mean glucose value from baseline to EOS
- Time in different ranges (% of SG): SG < 54 mg/dL, SG < 70 mg/dL, 70 mg/dL  $\leq$  SG  $\leq$  140 mg/dL, SG > 140 mg/dL, 180 mg/dL, 250 mg/dL, and 350 mg/dL
- Number of Events, Area Under Curve (AUC) and Time in the hyperglycemic range: SG > 140 mg/dL, 180 mg/dL, 250 mg/dL, and 350 mg/dL
- Number of Events, AUC and Time in the hypoglycemic range: SG < 54 and 70 mg/dL
- Change in BG values during meal/exercise challenge (BG prior and BG 2 hours after meal/exercise)
- Change in % of time in euglycemia 70-180 mg/dL during meal/exercise challenge, prior and 2 hours after meal/exercise
- Difference in AUC during meal challenge prior and 2 hours after meal/exercise
- Change of Total Daily Dose (TDD) of insulin from baseline to EOS Period
- Change of weight from baseline to EOS Period
- Subgroup analysis will be performed for:
  - Setpoint

D00409632 Version E Page 93 of 106 Medtronic

- 100 ma/dL
- 110 mg/dL
- 120 mg/dL
- 150 mg/dL (Temp Target Usage)

#### **14.4.3 Safety Data Summarized**

- Serious Adverse Events (SAE)
- Serious Adverse Device Effects (SADE)
- Unanticipated Adverse Device Effects
- Incidence of Severe Hypoglycemia
- Incidence of Severe Hyperglycemia
- Incidence of DKA

#### 14.4.4 Device Deficiencies

Descriptive summary will be used to characterize device deficiencies:

All reports of device issues.

#### 14.4.5 Subject Feedback

Descriptive summary will be used to characterize study questionnaire results. Refer to CIP335 Lyumjev -Questionnaire Guide for administration details.

### 14.5 Sample Size Considerations/Sample Size Justification

#### 14.5.1 Age 18-80

• Sample size for the primary safety endpoint: the overall mean change in HbA1c from baseline to end of 3-month study period

The overall mean change in HbA1c from baseline to end of 3-month study period from 670G (CEP294 HCL age 18 to 75, N = 101) study was -0.50%. Assuming the mean change in HbA1c from baseline to end of 3-month study period from 780G is the same as 670G, with a standard deviation of 0.7%, SAS power and sample size calculator with one sample T test shows that a total of 80 subjects will provide > 80% power, to detect that mean HbA1c is less than -0.50% with a margin of 0.4% at a significance level of 0.025 (one-sided).

Sample size for the primary effectiveness endpoint: the mean % of time in range (TIR 70-180 mg/dL)

The mean % of time in target from 670G (CEP294 HCL age 18 to 75, N = 104) study was 73.7%. Assuming the mean time in target (%) from 780G is the same as 670G, with a standard deviation of 8.8%, SAS power and sample size calculator with one sample T test shows that a total of 80 subjects will provide > 80% power, to detect that mean % of time in target is greater than 73.7% with a margin of -7.5% at a significance level of 0.025 (one-sided).

Sample size for the secondary effectiveness endpoint: the mean % of time below range (< 54 mg/dL)

The mean % of time below range (< 54 mg/dL) from 670G (CEP294 HCL age 18 to 75, N = 104) study was 0.86%. Assuming the mean time below target (%) from 780G is the same as 670G, with a standard deviation of 0.79%, SAS power and sample size calculator with one sample T test shows that a total of 80 subjects will provide > 80% power, to detect that mean % of time below range is less than 0.86% with a margin of 2% at a significance level of 0.025 (one-sided).

Sample size for the secondary effectiveness endpoint: the mean % of time in range (TIR 70-180 mg/dL)

The mean % of time in target from 670G (CEP294 HCL age 18 to 75, N = 104) study was 73.7%. Assuming the mean time in target (%) from 780G is 76%, with a standard deviation of 7.2%, SAS power and sample size calculator with one sample T test shows that a total of 80 subjects will provide > 80% power, to detect that mean % of time in target is greater than 73.7% at a significance level of 0.025 (one-sided).

#### 14.5.2 Age 7-17

Sample size for the primary safety endpoint: the overall mean change in HbA1c from baseline to end of 3-month study period

The overall mean change in HbA1c from baseline to end of 3-month study period from 670G (CEP294 and CEP302 HCL age 7 to 17, N = 125) study was -0.38%. Assuming the mean change in HbA1c from baseline to end of 3-month study period from 780G is the same as 670G, with a standard deviation of 0.7%, SAS power and sample size calculator with one sample T test shows that a total of 80 subjects will provide > 80% power, to detect that mean change of HbA1c is less than -0.38% with a margin of 0.4% at a significance level of 0.025 (one-sided).

Sample size for the primary effectiveness endpoint: the mean % of time in range (TIR 70-180 mg/dL)

The mean % of time in target from 670G (CEP294 and CEP302 HCL age 7 to 17, N = 125) study was 65.3%. Assuming the mean time in target (%) from 780G is the same as 670G, with a standard deviation of 8%, SAS power and sample size calculator with one sample T test shows that a total of 80 subjects will provide > 80% power, to detect that mean % of time in target is greater than 65.3% with a margin of -7.5% at a significance level of 0.025 (one-sided).

Sample size for the secondary effectiveness endpoint: the mean % of time below range (< 54 mg/dL)

The mean % of time below range (< 54 mg/dL) from 670G (CEP294 and CEP302 HCL age 7 to 17, N = 125) study was 0.71%. Assuming the mean time below target (%) from 780G is the same as 670G, with a standard deviation of 0.60%, SAS power and sample size calculator with one sample T test shows that a total of 80 subjects will provide > 80% power, to detect that mean % of time below range is less than 0.71% with a margin of 2% at a significance level of 0.025 (one-sided).

D00409632 Version E Page 95 of 106

Sample size for the secondary effectiveness endpoint: the mean % of time in range (TIR 70-180 mg/dL)

The mean % of time in target from 670G (CEP294 and CEP302 HCL age 7 to 17, N = 125) study was 65.3%. Assuming the mean time in target (%) from 780G is 67.5%, with a standard deviation of 7%, SAS power and sample size calculator with one sample T test shows that a total of 80 subjects will provide > 80% power, to detect that mean % of time in target is greater than 65.3% at a significance level of 0.025 (one-sided).

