### 6.2.2 Age 7-17

[figure not shown]
Sample size for the primary safety endpoint: the overall mean change in HbA1c from baseline to end of 3-month study period

The overall mean change in HbA1c from baseline to end of 3-month study period from 670G (CEP294 and CEP302 HCL age 7 to 17, N = 125) study was -0.38%. Assuming the mean change in HbA1c from baseline to end of 3-month study period from 780G is the same as 670G, with a standard deviation of 0.7%, SAS power and sample size calculator with one sample T test shows that a total of 80 subjects will provide > 80% power, to detect that mean change of HbA1c is less than -0.38% with a margin of 0.4% at a significance level of 0.025 (one-sided).

Sample size for the primary effectiveness endpoint: the mean % of time in range (TIR 70-180) mg/dL)

The mean % of time in target from 670G (CEP294 and CEP302 HCL age 7 to 17, N = 125) study was 65.3%. Assuming the mean time in target (%) from 780G is the same as 670G, with a standard deviation of 8%, SAS power and sample size calculator with one sample T test shows that a total of 80 subjects will provide > 80% power, to detect that mean % of time in target is greater than 65.3% with a margin of -7.5% at a significance level of 0.025 (one-sided).

20-DEC-2023 Page 15 of 25 Revision 3.0

Sample size for the secondary effectiveness endpoint: the mean % of time below range (< 54 mg/dL)

The mean % of time below range (< 54 mg/dL) from 670G (CEP294 and CEP302 HCL age 7 to 17, N = 125) study was 0.71%. Assuming the mean time below target (%) from 780G is the same as 670G, with a standard deviation of 0.60%, SAS power and sample size calculator with one sample T test shows that a total of 80 subjects will provide > 80% power, to detect that mean % of time below range is less than 0.71% with a margin of 2% at a significance level of 0.025 (one-sided).

Sample size for the secondary effectiveness endpoint: the mean % of time in range (TIR 70-180 mg/dL)

The mean % of time in target from 670G (CEP294 and CEP302 HCL age 7 to 17, N = 125) study was 65.3%. Assuming the mean time in target (%) from 780G is 67.6%, with a standard deviation of 7%, SAS power and sample size calculator with one sample T test shows that a total of 80 subjects will provide > 80% power, to detect that mean % of time in target is greater than 65.3% at a significance level of 0.025 (one-sided).

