#### 7.1.4 **Analysis Sets**

### • Intention to Treat (ITT) Population

The ITT population will include all subjects who start the study period. Primary safety, primary effectiveness, secondary effectiveness and descriptive endpoints will be evaluated for ITT population.

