## 7.9.3 Analysis of Effectiveness Endpoint

All effectiveness endpoints will be analyzed using the data from the visit 13 to the end of the study (Auto Basal target set at investigator's discretion).

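### Protocol 14.5.2 and SAP 6.2.2 assume different pediatric means (67.5% and 67.6%) for the time-in-range superiority test, and at n = 80 the Protocol's value gives 79.3% power, marginally short of the stated > 80%

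*Protocol*

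**What the plan says.** Both documents size a secondary test of whether pediatric mean time in range (70-180 mg/dL) exceeds the 670G reference of 65.3%, with no margin.

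- Protocol 14.5.2: "Assuming the mean time in target (%) from 780G is 67.5%, with a standard deviation of 7" (per cent).
- SAP 6.2.2: "Assuming the mean time in target (%) from 780G is 67.6%, with a standard deviation of 7" (per cent).

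The remaining inputs agree: reference 65.3%, SD 7%, 80 subjects and a one-sided level of 0.025. The method and claim also agree. In the Protocol's words: "SAS power and sample size calculator with one sample T test shows that a total of 80 subjects will provide > 80% power". The SAP makes the same statement.

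Protocol 8.1 and SAP 6.1 plan for at least 200 subjects to enter the study period, with an enrolment goal of at least 100 in each age cohort. SAP 7.5.2 places this test last in the pediatric fixed sequence. SAP 7.9.1 bases study success on the primary endpoints.

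**The concern.** The two means give differences from the reference of 2.2 and 2.3 points. Both documents name the same test and the same 80 subjects, and both claim more than 80% power. A difference of 2.2 points with SD 7% and n = 80 is close to the boundary, so the 0.1-point mismatch could decide whether the claim is true.

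Two things are at stake. The documents disagree on a design input, so a reader cannot tell which assumption was intended. And one of the two power statements may not follow from its own inputs. This is a matter of accuracy in the sample-size sections. It does not bear on whether the trial can meet its primary objectives.

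**Working it through.** **Inputs.** Reference 65.3%, SD 7%, n = 80 and one-sided level 0.025 (Protocol 14.5.2 and SAP 6.2.2). Assumed mean 67.5% (Protocol) or 67.6% (SAP). Method: one-sample t test, as both documents name.

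**Formula.** Power = P(T > c), where T is noncentral t with n - 1 degrees of freedom and noncentrality difference × √n / SD, and c is the 97.5th percentile of the central t distribution. For n = 80, c = 1.9905 on 79 degrees of freedom.

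**The plan's own figures at n = 80.**

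| Source | Difference | Noncentrality | Power |
|---|---|---|---|
| Protocol | 67.5 - 65.3 = 2.2 | 2.2 × √80 / 7 = 2.811 | 79.3% |
| SAP | 67.6 - 65.3 = 2.3 | 2.3 × √80 / 7 = 2.939 | 82.7% |

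The SAP's claim is met. The Protocol's is missed by 80.0 - 79.3 = 0.7 points.

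**Subjects needed for 80%.** With the Protocol's inputs, power is 79.8% at 81 and 80.3% at 82, so 82 are needed. With the SAP's inputs, 75 are enough.

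**A different formula.** The normal approximation for the Protocol's inputs is Φ(2.811 - 1.960) = 80.3%. It would support the claim, but it is not the test named.

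**Rounding of the printed inputs.** With SD 7% and n = 80, power reaches 80% at a difference of 2.22, that is, a mean of 67.52%, which prints as 67.5%. With the difference held at 2.2, an SD of 6.93% gives 80.1%, and 6.93% prints as 7%. Rounding can also go the other way: a difference of 2.15 (mean 67.45%) gives about 77%, and an SD of 7.1% gives 78.2%.

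**At the planned size.** With n = 100, the noncentrality is 2.2 × 10 / 7 = 3.143 and power is 87.5% for the Protocol's mean. For the SAP's mean it is 2.3 × 10 / 7 = 3.286 and power is 90.2%.

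**The case against.** The strongest defence is that nothing of substance is wrong. The shortfall is 0.7 points, or two subjects. An unrounded mean of 67.52% or an unrounded SD of 6.93% would make the Protocol's statement true while printing exactly as it does. About 100 children, not 80, are planned to enter the study period. All of this stands, and it limits the point to a minor one. It does not remove the mismatch: 67.5% and 67.6% remain different printed assumptions for one calculation, and a reader who checks the Protocol's figure with the test it names gets 79.3%.

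A reader might go further and infer that the superiority power was helped by an unduly small SD. The primary time-in-range calculation for children reads "Assuming the mean time in target (%) from 780G is the same as 670G, with a standard deviation of 8" (per cent), and for adults "Assuming the mean time in target (%) from 780G is the same as 670G, with a standard deviation of 8.8" (per cent). The superiority calculations use 7% for children and, for adults, "Assuming the mean time in target (%) from 780G is 76%, with a standard deviation of 7.2" (per cent). The analysis set is common to both tests (SAP 7.1.4: "Primary safety, primary effectiveness, secondary effectiveness and descriptive endpoints will be evaluated for ITT population"), and so is the window (SAP 7.9.3: "All effectiveness endpoints will be analyzed using the data from the visit 13 to the end of the study").

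The documents do not support calling this an error. The two calculations describe different scenarios, one in which 780G performs like 670G and one in which it performs better, and each SD is paired with its own assumed mean. A common set and window do not show which SD is the better forecast. Neither document expressly sources any of these SDs, including the larger ones, so the lack of a citation does not single out the smaller values. The adult superiority claim is correct on its stated inputs: 2.3 × √80 / 7.2 = 2.857 gives 80.6%. Asking for the source of the SDs would be a reasonable request for justification, but it is a separate matter from this point.

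**Conclusion.** The point holds as a minor inconsistency. The Protocol and SAP print different pediatric means for the same test. At the printed values, the Protocol's claim of more than 80% power at n = 80 is marginally wrong (79.3%), and the SAP's is right (82.7%).

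This rests on treating the printed inputs as exact and on the one-sample t test that both documents name. It does not show which mean was intended.

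A reader might infer that the pediatric cohort is underpowered or that enrolment should rise. The documents do not support that. At about 100 children the Protocol's own inputs give 87.5%, and the shortfall arises only if fewer than 82 are evaluable. Protocol 14.5.3 gives no numeric drop-out rate and CGM endpoints are not imputed, so 100 evaluable children are not guaranteed. Even so, the test is the last secondary step and cannot change the cohort's pass or fail result.

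**What to change.** Use one pediatric mean in Protocol 14.5.2 and SAP 6.2.2, and restate the power at n = 80 to match: 79.3% if the mean is 67.5%, or 82.7% if it is 67.6%. Optionally add the power at the planned 100 per cohort: 87.5% or 90.2% respectively. If the calculation used unrounded inputs, print them to enough decimals for the claim to be reproduced.

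The cost is a wording change in one paragraph of the SAP or the Protocol, or both. No subjects, procedures, tests or success criteria change.
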